5.4 Statistical models

5.4.1 Primary analysis

The LIFETEST procedure in SAS with the TIME statement including a variable with survival times and a (right) censoring variable, and with STRATA statement including variables of stratification factors and with GROUP option under STRATA statement. As an output of the procedure, the rank statistic S and variance $\text{var}(S)$ will be obtained. Under the null hypothesis, the test statistic $Z=S/\sqrt{[\text{var}(S)]}$ is approximately normally distributed. The one-sided p -value will be obtained from normally distributed Z statistic.

This Section gives additional details regarding the analyses described in [Section 2.5.2](#).

Kaplan-Meier estimates

An estimate of the survival function in each treatment arm will be constructed using Kaplan-Meier (product-limit) method as implemented in PROC LIFETEST with METHOD=KM option. The PROC LIFETEST statement will use the option CONFTYPE=LOGLOG.

Median survival for each treatment arm will be obtained along with 95% confidence intervals calculated from PROC LIFETEST output using the method of ([Brookmeyer and Crowley 1982](#)). Kaplan-Meier estimates of the survival function with 95% confidence intervals at specific time points will be summarized. The standard error of the Kaplan-Meier estimate will be calculated using Greenwood's formula ([Collett 1994](#)).

Hazard ratio

Hazard ratio will be estimated by fitting the Cox proportional hazards model using SAS procedure PHREG (with TIES=EXACT option in the MODEL statement).

A stratified unadjusted Cox model will be, i.e. the MODEL statement will include the treatment arm variable as the only covariate and the STRATA statement will include stratification variable(s).

Hazard ratio with two-sided 95% confidence interval will be based on Wald test.

Treatment of ties

The STRATA statement in LIFETEST procedure will be used to analyze time to event data with ties. The PHREG procedure in SAS with option TIES=EXACT will be used to fit the Cox proportional hazards model.

Checking proportionality of hazard assumption

Plots (SURVIVAL LOGSURV LOGLOGS) generated by LIFETEST procedure in SAS will be used to provide visual checks of the proportional hazard assumption.

- LOGLOGS plots log (cumulative hazard). The LOGLOG plot will show parallel curves if hazards

are proportional.

5.4.2 Key secondary analysis

Same statistical methodologies will be used as in the primary efficacy analysis

5.5 Patient reported outcomes: EORTC QLQ-C30/LC13 and EQ-5D-5L/VAS

The text below gives more detailed instructions and rules needed for programming of the analyses described in [Section 2.11](#).

EORTC QLQ-C30 scale scores will be generated by first obtaining the raw scores adding up the item responses on the questions which make up each domain and then applying the linear transformation to the raw scores in accordance with the respective scoring manual provided by the developers. Scores in each scale will be generated if at least half of the items comprising the scale have been answered. For single item scales with missing responses and scales where less than half of the items have not been answered, scale scores will be set to missing.

The scoring approach for the QLQ-LC13 is identical in principle to that for the symptom scales/single items of the QLQ-C30. The dyspnea scale of the QLQ-LC13 is the only multi item scale (all others are single item scales) and should only be used if all items comprising the scale have been answered.

For the calculation of EQ-5D-5L index value, the EQ-5D crosswalk value set for the UK using the time trade-off method will be used. If any one of the five dimensions of health state is missing, the index value will be set to missing.

A repeated measures model for longitudinal data will be used to compare the two treatment arms in terms of the domain scores over time. This longitudinal model will include terms for treatment, the randomization stratification factors, time of visit (duration in days from the time of baseline measurement to the time of a particular post baseline measurement), baseline value as fixed effects, and an interaction term for treatment by time. This analysis will be restricted to subjects with an evaluable baseline score and at least one evaluable post-baseline score. Time will be considered as a continuous variable in this analysis. As a first approach, an unstructured correlation matrix will be used to model the correlation within subjects. Other structures of the correlation matrix, including AR (1), will be investigated and simplified using likelihood ratio tested if appropriate. In particular situations, the non-convergence of the model may be caused by few subjects with assessments at later time points. The possibility of removing few assessments later than a certain time point will be investigated if appropriate.

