7.2.6 Patient reported outcomes

7.2.6.1 PRO Questionnaires

The European Organization for Research and Treatment of Cancer's core quality of life questionnaire EORTC-QLQC30 (version 3.0) and it's lung cancer specific module QLQ-LC13 (version 1.0) will be used to collect data on the subject's functioning, disease-related symptoms, health-related quality of life, and health status. The EQ-5D-5L will be used for the purpose of the computation of utilities that can be used in health economic studies. The EORTC QLQ-C30/LC13 as well as the EQ-5D-5L are reliable and valid measures frequently used in clinical

trials of subjects with lung cancer and previously used in the adjuvant setting (Bezjak et al 2008).

The EORTC-QLQC30 is a self-reporting 30-item generic instrument for use in cancer subjects across tumor types including lung cancer. It assesses 15 domains consisting of 5 functional domains (physical, role, emotional, cognitive, social) and 9 symptom domains (fatigue, nausea and vomiting, pain, dyspnea, insomnia, appetite loss, constipation, diarrhea, financial difficulties) and a global health status or HRQoL scale (Aaronson et al 1993). The EORTC QLQ-LC13 complements the QLQ-C30, and measures disease symptoms and treatment-related adverse effects. The lung cancer module incorporates one multi-item scale to assess dyspnea, and 9 single items assessing pain, coughing, sore mouth, dysphagia, peripheral neuropathy, alopecia, and hemoptysis (Bergman et al 1994).

All of the domain scores of the EORTC-QLQC30 and QLQ-LC13 range from 0 to 100. A high score indicates a higher response level. Hence, a high score for a functional scale indicates a high and healthy level of functioning but a high score for a symptom scale indicates a high level of symptoms/problems.

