10.5.6 Patient-reported outcomes

Three patient-reported outcomes (PRO) questionnaires will be assessed: EORTC QLQ-C30 with QLQ-LC13 incorporated and the EQ-5D-5L. QLQ-C30 and QLQ-LC13 will be considered as the primary scale. Scoring of PRO data and methods for handling of missing items or missing assessments will be handled according to the scoring manual and user guide for each respective subject questionnaire (Fayers 2001, Van Reenen 2015). No imputation procedures will be applied for missing items or missing assessments.

The FAS will be used for analyzing PRO data. Time to definitive 10 point deterioration symptom scores of pain, cough and dyspnea per QLQ-LC13 questionnaire are primary PRO variables of interest. Time to first 10 point deterioration symptom scores of pain, cough and dyspnea per QLQ-LC13 questionnaire, time to first 10 point deterioration of global health status/QoL, shortness of breath and pain per QLQ-C30 questionnaire, time to 10 point definitive deterioration of global health status/QoL, shortness of breath status/QoL, shortness of breath and pain per QLQ-C30 together with the utilities derived from EQ-5D-5L are secondary PRO variables of interest.

Confidential

[figure not shown]
Time to deterioration in symptoms and in global health status/QoL are defined as follows:

- The time to definitive 10 point deterioration is defined as the time from the date of randomization to the date of event, which is defined as at least 10 points absolute increase from baseline (worsening) of the corresponding scale score, with no later change below this threshold i.e. < 10 points was observed or if this increase was observed at the last assessment for the subject, or death due to any cause, whichever occurs earlier. If a subject has not had an event, time to definitive deterioration will be censored at the date of the last adequate assessment. The distribution will be presented descriptively using Kaplan-Meier curves. Summary statistics from Kaplan-Meier distributions will be determined, including the median time to definitive 10 point deterioration along with two-sided 95% confidence interval. Additionally, time to definitive deterioration with different definition for deterioration may be specified in the SAP as deemed appropriate. A stratified Cox regression will be used to estimate the hazard ratio (HR), along with two-sided 95% confidence interval.

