2.11 Patient-reported outcomes

Three patient-reported outcomes (PRO) questionnaires will be assessed: EORTC QLQ-C30, with its QLQ-LC13 lung cancer module, and the EQ-5D-5L. QLQ-C30 and QLQ-LC13 will be considered as the primary scale. Scoring of PRO data and methods for handling of missing items or missing assessments will be handled according to the scoring manual and user guide for each respective patient questionnaire ([Fayers 2001](#), [Van Reenen 2015](#)). No imputation procedures will be applied for missing items or missing assessments.

The FAS will be used for analyzing PRO data. For all PRO analysis, nominal *p*-values will be presented without any statistical inference since there is no adjustment for multiplicity. The baseline is defined as the last PRO assessment on or prior to randomization. In the absence of a better definition

to define clinically relevant changes in this population (lung cancer, adjuvant setting) a 10 point deterioration will be assumed to be clinically meaningful for the QLQ-LC13 and QLQ-C30 (Osoba 1998).

The primary PRO variables of interest are: time to definitive 10 point deterioration symptom scores for each of chest pain, cough and dyspnea per QLQ-LC13 questionnaire

The secondary PRO variables of interest are:

- Utilities derived from the EQ-5D-5L
- Time to first 10 point deterioration symptom scores of pain, cough and dyspnea per QLQ-LC13 questionnaire
- Time to first 10 point deterioration of global health status/QoL, shortness of breath, pain, role functioning, physical functioning and fatigue per QLQ-C30 questionnaire
- Time to 10 point definitive deterioration in global health status/QoL, shortness of breath, pain, role functioning, physical functioning and fatigue per QLQ-C30

The time to 10 point definitive deterioration is defined as the time from the date of randomization to the date of event, which is defined as at least 10 points absolute worsening from baseline of the corresponding scale score, with no later change below this threshold, i.e. <10 points was observed or if this worsening was observed at the last assessment for the subject, or death due to any cause (whichever occurs earlier).

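### A stray *not* in SAP 5.5 reverses the missing-item rule for multi-item QLQ-C30 scales and contradicts the sentence before it

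*SAP*

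**What the plan says.** SAP 5.5 opens by stating its purpose: "The text below gives more detailed instructions and rules needed for programming of the analyses described in" SAP 2.11. It says QLQ-C30 raw scores are the summed item responses of each domain, linearly transformed in line with the developers' scoring manual. Two rules for unanswered items follow in consecutive sentences:

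- Rule A: "Scores in each scale will be generated if at least half of the items comprising the scale have been answered".
- Rule B: a single-item scale with no response is missing and, for "scales where less than half of the items have not been answered, scale scores will be set to missing".

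The same section treats the QLQ-LC13 separately. Dyspnea is its only multi-item scale, and it "should only be used if all items comprising the scale have been answered".

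Elsewhere the documents point to outside references. SAP 2.11 says "methods for handling of missing items or missing assessments will be handled according to the scoring manual and user guide for each respective patient questionnaire", and protocol 10.5.6 says the same: "Scoring of PRO data and methods for handling of missing items or missing assessments will be handled according to the scoring manual and user guide". Neither restates a half rule, so SAP 5.5 is the only place where it is written out.

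The secondary PRO variables in SAP 2.11 include "Time to 10 point definitive deterioration in global health status/QoL, shortness of breath, pain, role functioning, physical functioning and fatigue per QLQ-C30", together with time to first deterioration on the same QLQ-C30 scales.

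**The concern.** Rule B is plainly meant to be the complement of Rule A: one says when a score exists, the other when it does not. As worded it is close to a reversal. A scale with fewer than half of its items unanswered has more than half answered, which is a scale that Rule A scores. A fully answered scale, with none unanswered, also meets the condition for being set to missing.

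The sentence stands in the text that a programmer works from. SAP section 5 also says that the appendix will be reused for the statistical appendix of the study report, and the close-out SAP lists the QLQ-C30 score summary again (Table 14.2-5.1). If the clause were coded literally, complete multi-item scores would be lost from those summaries, from the change-from-baseline tables, and from the repeated measures model, which requires an evaluable baseline score and at least one evaluable post-baseline score.

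**Working it through.** There is no stated figure to reproduce. The check sets the two sentences side by side.

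**Inputs.** Rules A and B are from SAP 5.5. The documents do not give the number of items per QLQ-C30 scale. Protocol 7.2.6.1 says "The EORTC-QLQC30 is a self-reporting 30-item generic instrument" and counts 15 domains (5 functional, 9 symptom, 1 global). With 30 items in 15 domains, at least one domain must hold more than one item. Which ones do is not stated. I assume sizes from 1 to 5 items and check all of them.

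**Notation.** A scale has k items, a answered and u = k − a unanswered.

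- Rule A: score if a ≥ k/2.
- Rule B, literal, for k ≥ 2: missing if u < k/2. Substituting u = k − a gives k − a < k/2, that is a > k/2.
- Rule B for k = 1: missing if u = 1.

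So for any multi-item scale, the patterns that Rule B sets to missing (a > k/2) all lie inside the patterns that Rule A scores (a ≥ k/2). This holds whatever the scale size.

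**Enumeration** (entries are answered/total):

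| k | Conflict: A scores, B sets to missing | Gap: A does not score, B does not set to missing | Consistent |
|---|---|---|---|
| 1 | none | none | 0/1, 1/1 |
| 2 | 2/2 | 0/2 | 1/2 |
| 3 | 2/3, 3/3 | 0/3, 1/3 | none |
| 4 | 3/4, 4/4 | 0/4, 1/4 | 2/4 |
| 5 | 3/5, 4/5, 5/5 | 0/5, 1/5, 2/5 | none |

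There are 2 + 3 + 4 + 5 + 6 = 20 patterns. Conflicts: 1 + 2 + 2 + 3 = 8. Gaps: 1 + 2 + 2 + 3 = 8. Consistent: 2 + 1 + 0 + 1 + 0 = 4. Without the 2 single-item patterns, 16 of 18 multi-item patterns are in conflict or gap, and the 2 that agree are those with exactly half answered. These are counts of possible patterns, not of expected forms. In practice the pattern that matters most is the complete scale, and it falls in the conflict column for every multi-item size.

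**After deleting *not*.** Rule B becomes: missing if a < k/2, the exact complement of Rule A. All 20 patterns are then consistent, with no conflict and no gap.

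**Reach.** The primary PRO variables are QLQ-LC13 pain, cough and dyspnea (SAP 2.11). By SAP 5.5, pain and cough are single-item scales, which Rule B handles correctly, and dyspnea has its own all-items rule. Only multi-item QLQ-C30 scores are exposed.

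**The case against.** The best defence is that nobody would program this. The sentence before gives a complete and workable rule, the clause is a double negative that obviously went wrong, and the scoring manual is named as the authority in SAP 5.5, SAP 2.11 and protocol 10.5.6. A program that deleted every fully answered multi-item scale would leave those tables nearly empty, and the first dry run would show it. All of this stands, and it is why the point is minor. It does not make the sentence right: it is an operative rule in the programming section, and no other section writes the half rule out correctly.

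A reader might also infer that lost scores would trigger the rule in SAP 2.11 that censors a definitive deterioration seen after two or more missing assessments. The documents do not support that step. The half rule works on a scale, while the censoring rule refers to assessments and to the last available questionnaire. The SAP does not say that a completed questionnaire with one unscored scale counts as a missing assessment.

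Nor do the documents support a definite list of affected variables. Physical functioning, role functioning, fatigue, pain and global health status may be taken to be multi-item, but the documents give no item counts per QLQ-C30 scale.

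**Conclusion.** The clause is wrong as written and contradicts the sentence before it. Taken literally, it sets complete and mostly complete multi-item QLQ-C30 scales to missing and does not catch those with fewer than half of the items answered. The contradiction holds for any scale of two or more items; only the pattern counts rest on the assumed sizes of 1 to 5.

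The consequence is small. It is a drafting slip, not a choice of analysis, and harm requires literal programming. A reader might conclude that complete questionnaires were in fact discarded, or that the PRO results are unsound. Nothing in the documents shows which rule the scoring program used, so neither conclusion follows. The exposed endpoints are secondary PRO variables, for which SAP 2.11 gives nominal p-values without inference and without multiplicity adjustment. DFS, OS and the primary PRO variables are unaffected.

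**What to change.** Delete *not* from the clause in SAP 5.5, so that it sets to missing single-item scales without a response and multi-item scales with fewer than half of their items answered. As the SAP is final, an erratum or a note in the study report would do, with the corrected sentence carried into the report's statistical appendix. Confirm that the QLQ-C30 scoring program uses the at-least-half rule. The cost is one word and one code check; outputs would need rerunning only if the check shows that the literal clause was programmed.

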5.6 Missing tumor assessments

The term ‘missing adequate tumor assessment’ is defined as a tumor assessment not done. For the sake of simplicity, a ‘tumor assessment’ will be referred to as an ‘assessment’ and a ‘missing adequate tumor assessment’ will be referred to as a ‘missing assessment’.

The presence and the number of missing assessments affects DFS censoring and event date.

An exact rule to determine whether there is no, one or two missing assessments is therefore needed. This rule is based:

- on the duration between LATA date and the event date
- on the duration between LATA date and the cut-off date

In this study, the protocol defined schedule of assessments is

- every 12 weeks during the first year (i.e. at weeks 12, 24, 36 and 48),
- every 26 weeks through year 2 and year 3 (i.e. at weeks 74, 100, 126 and 152),
- every 52 weeks through year 4 and year 5 (i.e. at weeks 204 and 256).

The scheduled date of assessments (in weeks from randomization), protocol specified windows for assessment, and the thresholds for LARA to belong to a visit can be found in [Table 5-3](#).

Table 5-3 Schedule for assessments, time windows and D1/D2 (weeks)

assessment schedule		Scheduled date – one week*	Schedule date (weeks from randomization)	Scheduled date + one week*	Threshold (weeks)**	Boundary of assessment*** (start, end]	D1/D2****
Every 12 weeks for the first year	1 st (C5D1)	11	12	13	18	(0,18]	14/26
	2 nd (C9D1)	23	24	25	30	(18,30]	14/26
	3 rd (C13D1)	35	36	37	42	(30,42]	14/40
	4 th (C17D1)	47	48	49	61	(42,61]	28/54
Every 26 weeks for the second and third year	5 th	73	74	75	87	(61,87]	28/54
	6 th	99	100	101	113	(87,113]	28/54
	7 th	125	126	127	139	(113,139]	28/80
	8 th	151	152	153	178	(139,178]	54/106
Every 52 weeks for the four and fifth year	9 th	203	204	205	230	(178,230]	54/106
	10 th	255	256	257	282	(230, 282]	54/106

* These start and end study weeks are used to determine if a visit is on schedule. For example, a visit between study week 23 and study week 25 is considered the 2nd ‘on schedule’ assessment.

** The threshold correspond to the mid-point between current and next visit and to the upper limit for LARA to be matched to a certain scheduled assessment e.g. if LARA is at week 45, this is after the threshold for 3rd recurrence assessment (C13D1) and before that for the 4th recurrence assessment, so the matching schedule assessment is the 4th recurrence assessment (C17D1).

*** These boundaries are defined according to assessment thresholds to calculate D1 and D2. For example: (30, 42] means any assessment falls into this time interval will be considered as the 3rd assessment visit.

**** D1 and D2 are defined per the protocol-specified recurrence assessment schedule

- The threshold D1 is defined as the protocol-specified time interval between the assessments plus 2x the protocol-allowed time window around the assessments (i.e. = 2*1 week=2 weeks).
- The threshold D2 is defined as twice the protocol-specified time interval between the assessments plus 2x the protocol-allowed time window around the assessments

Since there are changes in schedule for assessments during the 5 year tumor assessment period, D1 and D2 are defined differently depending on when LATA occurs. Here are the rules based on when LATA occurs:

- **Rule 1:** if LATA happens within 30 weeks after randomization (\leq study day 210 day), the applicable scheduled tumor assessments are the 1st and 2nd assessment (on C5D1 and C9D1), $D1 = 12 + 2 = 14$ weeks and $D2 = 12 * 2 + 2 = 26$ weeks.
- **Rule 2:** if LATA happens after 30 weeks but within 42 weeks, the matched scheduled tumor assessment is 3rd assessment (on C13D1), the study period: \geq study day 211 and \leq study day 294, $D1 = 12 + 2 = 14$ weeks and $D2 = 12 + 26 + 2 = 40$ weeks.
- **Rule 3:** if LATA happens after 42 weeks but within 113 weeks, the applicable scheduled tumor assessments are 4th, 5th and 6th assessments, the study period: \geq study day 295 and \leq study day 791, $D1 = 26 + 2 = 28$ weeks and $D2 = 26 * 2 + 2 = 54$ weeks.
- **Rule 4:** if LATA happens after 113 weeks but within 139 weeks, the matched scheduled tumor assessment is 7th assessment, the study period: ≥ 792 days and ≤ 973 days, $D1 = 26 + 2 = 28$ weeks and $D2 = 26 + 52 + 2 = 80$ weeks.
- **Rule 5:** if LATA happens after 139 weeks, the applicable scheduled tumor assessments are 8th, 9th and 10th assessments, the study period: ≥ 974 days, $D1 = 52 + 2 = 54$ weeks and $D2 = 52 * 2 + 2 = 106$ weeks.

The number of missing events is defined as:

- An event after LATA+D1 weeks will be considered as having ≥ 1 missing assessment
- An event after LATA+D2 weeks will be considered as having ≥ 2 missing assessments

6 Reference

1. Brookmeyer R and Crowley J (1982). A Confidence Interval for the Median Survival Time. *Biometrics*, 38, 29 - 41.
